8.2 SAFETY AND OTHER ASSESSMENTS

The Independent Medical Safety Monitor (IMSM) and the Data and Safety Monitoring Board (DSMB) will receive periodic safety reports of Adverse Events including Serious Adverse Events serious adverse events (SAEs) that have a reasonable possibility of being related to the study intervention following the reporting requirements of the University of Cincinnati Human Research Protection Program Policy 11.02. All reportable AEs will be summarized in terms of type of AE (AE code), when the AE occurred, frequency of the AE, number of subjects having the AE, severity of the AE, and relatedness to the study treatment. The proportion of subjects experiencing AEs will be provided in the closed report by treatment group arm with two-sided 95% CIs and unadjusted relative risks.

Safety analyses. Safety will be assessed by monitoring the rate of all clinical safety endpoints and SAEs throughout the treatment period. The proportion of children experiencing each of these events will be provided to the DSMB as unadjusted relative risks and 95% confidence intervals at regular intervals to facilitate decision making, but the trial does not provide binding statistical guidance on safety stopping.

In addition, the following measures of safety and tolerability will be assessed:

- Effects of continuous casting as noted in the daily logs by therapists, including recorded notes about the casted upper extremity during weekly cast removal to check for skin integrity, range-of-motion, and use of the casted upper extremity during 15-30 minutes of play (this is scored by the treating therapist).
- Stress in parents and infants related to the treatment or study participation as measured using the Perceived Stress Scale (for parents) and supplemental stress questions answered by parents about their child’s stress levels

We also include a set of measures for Exploratory Analyses.

Measures of child development for Exploratory Aim 3: Gross Motor Function Measure (GMFM-66) and the Bayley-4 Cognitive subtest. The GMFM-66⁷ measures gross motor function in children with cerebral palsy (5 mos - 16 yrs). 66 items are scored each on a 4-point scale and grouped into 5 domains (lying and rolling; sitting; crawling and kneeling; standing; and walking, running, and jumping); an overall GMFM Total Score also is computed. The GMFM-66 is considered valid and sensitive to changes in children with neuromotor impairment. We will use the Total Score in the exploratory analyses relating treatment group to gross motor development.

(One surgical intervention study¹²⁷ established a minimal clinically meaningful outcome on the GMFM-66 for older children as a gain of 2.7 points, although a gain of only 0.7 was deemed clinically useful for some patients. We will work with the Parent Council and clinicians to determine whether these (or other) thresholds might be suitable to consider for interpreting findings about GMFM-66 for children with PAIS.)

The Bayley Scales of Infant and Toddler Development-4 (Bayley-4) is the most widely used tool to assess infants (3 - 42 mos). It underwent major revision and re-norming in 2019, including children with disabilities.¹⁰⁷ It yields subtest scores for Fine Motor, Gross Motor, Language, Self-help, and Cognition and an overall Developmental Quotient (DQ). For Exploratory Aim 3, we primarily plan to use the Cognitive subtest (scores from 0 – 19, mean of 10, SD=3 pts) to consider whether one or both doses of I-ACQUIRE, compared to U&CT, are associated with significant gains in Cognition. We predict, based on theory, that the High Dose group will show larger mean cognitive gains than the children in the Moderate Dose or U&CT groups, and that likely these become detectable by the 6 mos. Post-Treatment Assessment. Our reasoning is if I-ACQUIRE produces large gains in UE skills (the primary and secondary efficacy outcomes), then treated children will be able to increase their successful interactions with their environment which, in turn, could improve their learning and problem-solving skills and lead to higher Bayley-4 Cognitive scores. Other subtests may also show benefits that will be considered in exploratory analyses.

Additional descriptive measures (not blinded) and rationale for collecting. We value the perspectives of parents about their children's response to treatment and their observations of their child's development. Parents have the greatest amount of experience with their child. They uniquely can provide ratings about what they observe in terms of their child's use of the hemiparetic UE in everyday settings and their participation in a wide variety of age-appropriate activities. Accordingly, parents will complete the Infant Motor Activity Log (IMAL),²⁶ a standardized tool about "how well" and "how often" their child uses the hemiparetic UE in 20 everyday behaviors (e.g., holding bottle/cup, eating finger foods, pushing a button, reaching to be picked up). The scale is 0 to 5 with behavioral anchoring provided. The IMAL will provide useful descriptive information to accompany the findings about primary and secondary efficacy. Parents also will complete the MacArthur-Bates Communicative Development Inventories (CDI),¹³⁰ a standardized reliable tool to assess the child's communicative competence. There is an infant version for 8 to 18 mos and a toddler version for 18 to 30 mos which can be used for older children who have shown language delay. Previous clinical observations of children treated with I-ACQUIRE indicate that children's language abilities may be improved by the treatment. Theoretically, this is important to understanding neuroplasticity and cross-domain changes after treatment. Parents also complete the Perceived Stress Scale at each assessment to monitor for parent response to treatment group and answer questions about their perceptions of their child's stress levels.

Clinical data about the infants: A Pediatric Neurology Exam will occur at each site at baseline by a trial-affiliated pediatric neurologist or physiatrist. It will include the Pediatric Stroke Outcome Measure (PSOM) (severity scores from 0 to 10), and information about co-morbidities, general health and health history, and the child's current and past treatments. These data will be used to describe the clinical sample and to compare subjects across treatment conditions and clinical sites.

NEUROIMAGING ANALYSIS: We will examine and code clinical MRI scans to yield a potentially useful set of imaging biomarkers that may predict differential responses to treatment (with implied underlying CNS mechanisms). The sites have agreed to use uniform imaging protocols for diagnosis of PAIS¹ (many already do this) to ensure that almost all MRI images will be consistently high quality. MRI scans will be reviewed by a pediatric neuroradiologist blinded to the subject's treatment at the Clinical MRI Core at Stanford. Coding will include summary measures about involvement of the hemispheres, basal ganglia (BG), posterior limb of the internal capsule (PLIC), and cerebral peduncle (CP). We will apply a previously described approach⁷ in which the path of the corticospinal tracts, including the posterior limb of the PLIC and the CP will be graded as "involved" or "not involved." In addition, we will classify brain regions as being (0) non-affected by the infarct, (1) <50% affected, (2) >50% affected, or (3) completely infarcted. Finally, we will calculate infarct volume by delineating the infarct on each MRI slice, measuring the areas corresponding to these delineations, and then multiplying these areas by the slice thickness (plus the gap if any). Major regions of interest for exploratory analyses include the corticospinal tracts in relationship to UE skills (EBS and Mini AHA) at baseline and at 2 endpoints after

treatment; association with gross motor development (GMFM-66) at all 3 timepoints; and infarct volume of discrete brain regions in relationship to Bayley-4 Cognition at all 3 timepoints. Also, we will have the ability to explore, for example, whether patterns of these MRI measures (e.g., reliable clusters of scores from the above coding) show a predictive association with which subjects show higher or lower change scores for the primary and secondary efficacy outcomes. The results of these biomarker analyses could be clinically useful in treatment recommendations for individual patients.

Parents will be given a questionnaire at the 6 mos Post-Treatment Assessment that has been designed by the I-ACQUIRE Parent Council to learn about parents' experiences with the I-ACQUIRE trial, and to help inform future clinical trials research about important aspects of family preferences, needs, and values.

A 36-item survey was developed that covers three topics: experience with the I-ACQUIRE trial; parents' values and preferences concerning child activities and participation in life situations; parents' experience in general with clinical trials. Participant ID will be the only identifier; no PHI is included on the survey.

The parent survey will be provided to parents with a cover letter from the Parent Council and envelope for returning the survey. Families will complete the survey just prior to and at the 6 mos Post-Treatment Assessment.

8.3 ADVERSE EVENTS AND SERIOUS ADVERSE EVENTS

8.3.1 DEFINITION OF ADVERSE EVENTS (AE)

Adverse events (AEs) are considered to be any undesirable sign, symptom, or medical condition occurring during the study, whether or not related to the intervention. AEs include new events not present prior to intervention (i.e., at screening AEs), can be spontaneously reported or elicited during open-ended questioning, examination, or evaluation of a subject

(See below for additional information about coding the type, severity, and relationship of an AE to study intervention for this trial.)

8.3.2 DEFINITION OF SERIOUS ADVERSE EVENTS (SAE)

An SAE is any untoward medical occurrence that:

- results in death;
- is life-threatening (defined as an event in which the participant was at risk of death at the time of the event; it does not refer to an event which hypothetically might have caused death if it were more severe);
- requires inpatient hospitalization or causes prolongation of existing hospitalization;
- results in persistent or significant disability/incapacity;
- is a congenital anomaly/birth defect;
- is an important medical event (defined as a medical event(s) that may not be immediately life-threatening or result in death or hospitalization but, based upon appropriate medical and scientific judgment, may jeopardize the subject or may require intervention [e.g., medical, surgical] to prevent one of the other serious outcomes listed in the definition above.)

The definition of SAE excludes the following hospitalizations:

- A visit to the emergency room or other hospital department < 24 hours, that does not result in admission (unless considered an important medical or life-threatening event);
- Elective surgery, planned prior to signing consent;
- Admissions as per protocol for a planned medical/surgical procedure;

- Routine health assessment requiring admission for baseline/trending of health status (e.g., routine colonoscopy);
- Medical/surgical admission other than to remedy ill health and planned prior to entry into the study (appropriate documentation is required in these cases);
- Admission encountered for another life circumstance that carries no bearing on health status and requires no medical/surgical intervention (e.g., lack of housing, economic inadequacy, caregiver respite, family circumstances, administrative reason).

8.3.3 CLASSIFICATION OF AN ADVERSE EVENT

8.3.3.1 SEVERITY OF EVENT

The severity of adverse events will be reported using the grading system outlined in the NCI Common Terminology Criteria for Adverse Events Version 4.03 (CTCAE). The CTCAE provides a grading (severity) scale for each AE term and AEs are listed alphabetically within categories based on anatomy or pathophysiology. The CTCAE (v4.03) displays Grades 1-5 with unique clinical descriptions of severity for each AE based on this general guidance:

CTCAE Severity Grading Summary	
Grade 1:	Mild AE
Grade 2:	Moderate AE
Grade 3:	Severe or Disabling AE
Grade 4:	Life-Threatening AE
Grade 5:	Death related to AE

The complete definitions of these grades are:

- Grade 1: Mild; asymptomatic or mild symptoms; clinical or diagnostic observations only; intervention not indicated AE.
- Grade 2: Moderate; minimal, local or noninvasive intervention indicated; limiting age-appropriate instrumental activities of daily living (preparing meals, shopping for groceries or clothes, using the telephone, managing money, etc.).
- Grade 3: Severe or medically significant but not immediately life-threatening; hospitalization or prolongation of hospitalization indicated; disabling; limiting self-care activities of daily living (bathing, dressing and undressing, feeding self, using the toilet, taking medications, and not bedridden).
- Grade 4: Life-threatening consequences; urgent intervention indicated.
- Grade 5: Death related to AE.

8.3.3.2 RELATIONSHIP TO STUDY INTERVENTION

One of the most important components of AE reporting is determining the cause of the AE. It is imperative that the site investigator assess AE causality in terms of overall study participation and make an independent determination as to whether the AE was thought to be related to any study-related activity (i.e., study intervention, test article administration, study-related tests or procedures). For the subjects in U&CT, AEs that occur cannot be considered to be related to study participation, since the child previously was receiving this form of treatment (i.e., parents agree not to change the child's U&CT during the study period). Further, the study has no authority to obtain data from the child's community therapist(s) and thus cannot infer likely relationship to the U&CT intervention. For each Adverse Event, the relationship to the study treatment must be recorded as one of the choices on the following scale:

NOT RELATED (MUST HAVE 1)

- Unreasonable or incompatible temporal relationship to the intervention
- Event is clearly due to extraneous causes (e.g., underlying disease, environment)

-
- UNLIKELY (MUST HAVE 2)**
 - Reasonable or tenuous temporal relationship to intervention
 - Could readily have been produced by the subject’s clinical state, or environmental or other interventions
 - Does not follow known pattern of response to intervention
 - Does not reappear or worsen with reintroduction of intervention
-
- REASONABLE POSSIBILITY (MUST HAVE 2)**
 - Reasonable temporal relationship to intervention
 - Could not readily have been produced by the subject’s clinical state or environmental or other interventions
 - Follows a known pattern of response to intervention
-
- DEFINITELY (MUST HAVE 4)**
 - Reasonable temporal relationship to intervention
 - Could not readily have been produced by the subject’s clinical state or have been due to environmental or other interventions
 - Follows a known pattern of response to intervention
 - Disappears or decreases with reduction in dose or cessation of intervention and recurs with re-exposure

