8.3.4 TIME PERIOD AND FREQUENCY FOR EVENT ASSESSMENT AND FOLLOW-UP

The occurrence of an adverse event (AE) or serious adverse event (SAE) may come to the attention of study personnel during study visits and interviews of a study participant presenting for medical care, or upon review by a study monitor. The following AEs will be reported in the study database: 1) Any serious AE (SAE) possibly related to study participation occurring from the Baseline assessment through the participant’s end of study; 2) Any AE occurring from the Baseline Assessment through the participant’s end of study that has a reasonable possibility of being related to study participation. All such events are captured on the appropriate CRF and entered into WebDCU™. Information to be collected for reportable adverse events includes event description, time of onset, clinician’s assessment of severity, relationship to study product (assessed only by those with the training and authority to make a diagnosis), and time of resolution/stabilization of the event.

Any medical condition that is present prior to Baseline Assessment will be considered as pre-existing or baseline and not reported as an AE. However, if the study participant’s condition deteriorates at any time during the study, and is possibly related to study intervention, it will be recorded as an AE.

Changes in the severity of an AE possibly related to study intervention will be documented to allow an assessment of the duration of the event at each level of severity to be performed. AEs characterized as intermittent require documentation of onset and duration of each episode.

Site PIs will record all reportable events consistent with the University of Cincinnati Human Research Protection Program Policy 11.02.

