8.3.5 ADVERSE EVENT REPORTING

All reporting is done in accordance with StrokeNet Standard Operating Procedures for Safety Monitoring and Reporting as outlined in the administrative documents available on the website (<https://www.nihstrokenet.org/docs/default-source/default-document-library/adm13-safety-monitoring-and->

reporting-12-19-16.pdf?sfvrsn=0). Clinical sites report all SAEs and any AEs that have a reasonable possibility of being related to the intervention into WebDCU™. These events are coded using MedDRA. Sites are required to report SAEs within 24 hours and non-serious AEs within 5 days of their awareness of the event.

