9.4.5 SAFETY ANALYSES

All reportable AEs and SAEs will be summarized by Meddra term and body system in terms of frequency of the event, number of subjects having the event, severity, and relatedness to the study treatment. The proportion of subjects experiencing each of these events will be provided in the closed report by treatment arm with two-sided 95% CIs and unadjusted relative risks. Fisher's exact tests will be used to assess treatment group differences in the rates of serious adverse events.

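### Non-serious adverse events in the U&CT arm are zero by rule, so relative risks against it are undefined, and the protocol contradicts itself on whether U&CT serious events are recorded

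*Protocol*

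**What the plan says.** Section 8.3.3.2 tells the site investigator to judge whether an event is "related to any study-related activity (i.e., study intervention, test article administration, study-related tests or procedures". The same paragraph then removes one arm from that judgement: "For the subjects in U&CT, AEs that occur cannot be considered to be related to study participation". Its reasons are that the child was already receiving this therapy, and that the study has no authority to obtain data from community therapists, so no link to U&CT therapy can be inferred either.

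Three sections say what is recorded:

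- Section 8.3.4 enters in the study database "Any serious AE (SAE) possibly related to study participation occurring from the Baseline assessment" up to the end of study, and any AE over the same period "that has a reasonable possibility of being related to study participation".
- Section 8.3.5 has a different rule: "Clinical sites report all SAEs and any AEs that have a reasonable possibility of being related to the intervention".
- Section 8.3.6 requires every SAE to be entered within 24 hours, with no relatedness condition. The independent medical safety monitor judges relatedness after entry.

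Two sections say what is done with the records. Section 8.2 describes the periodic reports to the safety monitor and DSMB as covering AEs, including SAEs, with a reasonable possibility of relatedness, and has the proportions "provided in the closed report by treatment group arm with two-sided 95% CIs and unadjusted relative risks". Section 9.4.5 repeats these summaries for reportable AEs and SAEs, and adds that Fisher's "exact tests will be used to assess treatment group differences in the rates of serious adverse events".

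**The concern.** A randomised control arm lets a safety comparison separate treatment harm from the illnesses, falls and injuries that occur at this age anyway. That works only if events enter the database by the same rule in every arm. Here the entry rule is relatedness, and one arm is barred from ever meeting it.

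Section 8.2 gives the DSMB the relative risks as an aid to decisions and sets no binding statistical rule for safety stopping, so these by-arm figures carry weight. If U&CT is zero by definition, a background event labelled related in an I-ACQUIRE arm looks like pure excess. Non-serious events judged unrelated in the I-ACQUIRE arms are lost too, so a misattribution there cannot be found later by comparing arms. Events never recorded may not be recoverable at the analysis.

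**Working it through.** The protocol states no AE or SAE rate and no safety power, so there is no figure of its own to reproduce. The check sets the rules side by side and then works out the consequence with the planned 80 children per arm (section 4.1).

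**Non-serious AEs.**
- Entry condition in 8.3.4: reasonable possibility of relation to study participation. In 8.3.5: the same, to the intervention.
- U&CT under 8.3.3.2: relation to participation is ruled out, and relation to U&CT therapy cannot be inferred.
- Recorded U&CT count: 0/80 under either section.
- Relative risk against U&CT: (x/80) ÷ (0/80), undefined for every x.
- Exact 95% interval for 0/80: the upper limit is 1 − 0.025^(1/80) = 0.045, giving 0 to 4.5%. This interval describes the recording rule, not an observed rate.

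**SAEs if 8.3.4 governs.** The U&CT count is again 0/80 by rule. With equal arms, the two-sided Fisher p-value for x/80 against 0/80 is 2 × C(80, x) ÷ C(160, x):
- x = 5: p = 0.059
- x = 6: p = 0.028
- x = 7: p = 0.014

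Six recorded SAEs in one I-ACQUIRE arm therefore reach p < 0.05 whatever happened in U&CT. If both I-ACQUIRE arms are pooled (x/160 against 0/80), 8 events give p = 0.055 and 9 give p = 0.031. Section 9.4.5 does not say which contrast is meant, so both are shown.

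The next table is an illustration with assumed rates. The true SAE rate is the same in one I-ACQUIRE arm and U&CT. The middle column supposes that every I-ACQUIRE event is recorded and no U&CT event is, so it shows P(X ≥ 6) for X ~ Bin(80, rate). It is an upper bound, because 8.3.4 also filters the I-ACQUIRE arms.

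| Assumed true rate | P(p < 0.05), U&CT fixed at zero | P(p < 0.05), all events recorded in both arms |
|---|---|---|
| 2% | 0.5% | 0.2% |
| 5% | 21% | 1.6% |
| 10% | 82% | 2.8% |

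**SAEs if 8.3.5 and 8.3.6 govern.** Every U&CT SAE is entered before relatedness is judged. The control count is an observed number and the Fisher test compares like with like. The sentence in 8.3.5 could be read with its relatedness clause covering SAEs as well, but 8.3.6 has no such clause.

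**Section 8.3.3.2 against itself.** It asks for relatedness to study tests and procedures. U&CT children have the blinded assessments at baseline, end of treatment and 6 months (4.1), the baseline neurology examination (8.2) and, with parental consent, the cheek swab (6.2.1). An event during one of these could be related to participation, yet the blanket exclusion forbids saying so. The reasons given concern U&CT therapy only and do not reach these procedures.

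**The case against.** The strongest reply is that the only planned hypothesis test is on SAEs, and that 8.3.6 is explicit: all SAEs, within 24 hours, with relatedness judged afterwards. Section 8.3.3.2 also requires relatedness to be recorded on a scale that includes unrelated and unlikely, which suggests that unrelated events are expected in the record. If 8.3.6 governs, the SAE test is sound. This stands, and it limits the SAE point to an unresolved contradiction. It does not remove the contradiction, because 8.3.4 is the section that defines database content, and 8.2 applies a relatedness filter to the reports that the DSMB receives.

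Second, six possibly related SAEs among 80 children would be a serious matter in any case. Section 2.2 reports no adverse events in Studies 1A and 4 and mainly minor skin irritation elsewhere. This also stands: at low rates the false-signal risk is small, as the 2% row shows.

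Third, the DSMB has other information: therapist logs and weekly cast checks, parent and child stress measures, and the safety monitor's review of each reported SAE. Comparisons of Moderate with High Dose are untouched by the U&CT rule. A reader might infer that harm could not be seen at all, and the protocol does not support that. What is lost is the comparison with U&CT for non-serious events, and possibly for SAEs.

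Fourth, recording only related non-serious AEs is a defensible choice for an intervention that section 2.3.1 regards as minimal risk. That is accepted. It is incompatible only with planning relative risks against an arm that the rule empties.

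**Conclusion.** The point holds in two parts. For non-serious AEs it follows from the text alone, with no assumption: U&CT is 0/80 by rule, and every relative risk against it is undefined. For SAEs, sections 8.2 and 8.3.4 conflict with 8.3.5 and 8.3.6, and which of them governs decides whether the Fisher test in 9.4.5 means anything.

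Two stronger readings are tempting. One is that all planned AE and SAE comparisons have a control arm fixed at zero; 8.3.5 and 8.3.6 contradict that for SAEs. The other is to quote a false-positive rate for tests on non-serious AEs; 9.4.5 plans Fisher tests for SAEs only, so such a rate would describe no planned analysis. The SAE rates in the table above are assumptions, since the protocol gives none.

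Efficacy endpoints and sample size are not affected. The protocol should be corrected because the fault changes what the safety analysis can conclude, but it does not threaten the trial's main result.

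**What to change.** 1. Amend 8.2 and 8.3.4 to agree with 8.3.5 and 8.3.6: every SAE is recorded and reported in all three arms regardless of relatedness. Remove the ambiguity in the 8.3.5 sentence.
2. State in 8.2 and 9.4.5 that the SAE relative risks and Fisher tests use all-cause SAEs.
3. Reword 8.3.3.2 so that an event arising from a study assessment or procedure can be judged related in U&CT.
4. Show relatedness-filtered non-serious AEs only within the two I-ACQUIRE arms (Moderate against High Dose), with no relative risk against U&CT.
5. If a comparison of non-serious AEs with U&CT is wanted, collect those events all-cause, with the same prompts and schedule in every arm.

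Items 1 to 4 cost protocol wording and CRF instructions. The SAE entry is already required by 8.3.6. Item 5 is a real resource decision: it adds data entry in all three arms over the 7 to 13 months of participation given in the synopsis, and the sponsor may reasonably decline it provided item 4 is adopted.

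### Non-serious adverse events in the U&CT arm are zero by rule, so the planned relative risks against U&CT cannot be interpreted; for SAEs the protocol contradicts itself on which events are recorded

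*Protocol*

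**What the plan says.** **Relatedness (8.3.3.2).** The site investigator must "make an independent determination as to whether the AE was thought to be related to any study-related activity", and the scope given includes "study-related tests or procedures". The next sentence but one in effect exempts the control arm: "For the subjects in U&CT, AEs that occur cannot be considered to be related to study participation". Two reasons are given. The child was already receiving this therapy and parents agree not to change it, and the study has no authority to obtain data from community therapists.

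**Recording of non-serious AEs.** Section 8.3.4 item 2 admits an AE to the database if it is one "that has a reasonable possibility of being related to study participation". Section 8.3.5 has sites enter "any AEs that have a reasonable possibility of being related to the intervention".

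**Recording of SAEs.** Section 8.3.4 item 1 covers "Any serious AE (SAE) possibly related to study participation occurring from the Baseline assessment" through the end of the child's study. Section 8.2 likewise describes the periodic safety reports in terms of SAEs that may be related to the intervention. Sections 8.3.5 and 8.3.6 say instead that sites enter all SAEs, and in 8.3.6 the independent medical safety monitor judges relatedness after entry.

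**Reporting.** Section 8.2: "The proportion of subjects experiencing AEs will be provided in the closed report by treatment group arm", with 95% CIs and unadjusted relative risks. Section 9.4.5, on AEs and SAEs: "The proportion of subjects experiencing each of these events will be provided in the closed report by treatment arm with two-sided 95% CIs", again with relative risks. Section 9.4.5 adds Fisher's exact test, for SAEs only.

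**The concern.** A between-arm comparison of adverse events needs the same recording rule in each arm. Here the filter is relatedness to study participation, and one arm is declared unable to pass it. What the display then shows for U&CT is a consequence of the rule and carries no information about how often those children had events.

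The rule also does not fit its own section. The causality question is put for any study activity, and U&CT children take part in study activities: the same blinded assessments at baseline, end of treatment and 6 months (4.1), for which 2.3.1 lists risks, and the cheek swab where parents consent (6.2.1). The two reasons given in 8.3.3.2 concern only the community therapy.

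At stake is the comparative AE table in the closed report. Section 8.2 says the event proportions and relative risks go to the DSMB to help it decide and that there is no binding statistical guidance on safety stopping, so the board has to read the table at face value. An event that was never recorded cannot be restored by an analysis plan.

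**Working it through.** The protocol states no AE rate or relative risk, so there is no figure of its own to reproduce. The check traces the rules and then illustrates them at the planned 80 children per arm (4.1).

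**Step 1: non-serious AEs.**

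| Section | Effect on a non-serious AE in a U&CT child |
|---|---|
| 8.3.3.2 | cannot be classed as related to study participation |
| 8.3.4 item 2 | not recorded, because not related to study participation |
| 8.3.5 | sites enter only AEs possibly related to the intervention |
| 8.2, 9.4.5 | counted as no event in the U&CT row |

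The U&CT count is therefore 0/80 by rule. With x children with events in an I-ACQUIRE arm, the relative risk is (x/80)/(0/80): undefined or infinite for x > 0, and 0/0 for x = 0. The exact (Clopper-Pearson) upper 95% limit for 0/80 is 1 − 0.025^(1/80) = 4.5%. That limit is correct for the number of recorded events but says nothing about the number that occurred. Moderate v High Dose does not use the U&CT row, so its relative risk can be computed.

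For scale: if U&CT events were recorded and 5% of those children had one (assumed), the chance of an empty row would be 0.95^80 = 1.7%; at 10% (assumed) it would be 0.02%. Under the current rule it is certain.

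**Step 2: SAEs, two readings.**

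- *8.3.5 and 8.3.6 govern:* U&CT SAEs are entered regardless of relatedness. The rate is not fixed at zero, and the relative risk and Fisher's test have their usual meaning.
- *8.3.4 item 1 governs:* the Step 1 chain applies to SAEs too, and Fisher's test compares a recorded count with a forced zero.

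**Step 3: what the second reading would do to the Fisher test.** Two-sided Fisher, one dose arm v U&CT: 5/80 v 0/80 gives p = 0.059, and 6/80 v 0/80 gives p = 0.028. Six events are enough. Suppose true SAE rates are equal in the two arms and every I-ACQUIRE event is judged possibly related. The chance of a spurious p < 0.05 is then P(X ≥ 6) for X ~ Binomial(80, rate):

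| Assumed true rate | P(X ≥ 6) |
|---|---|
| 1% | 0.02% |
| 2% | 0.5% |
| 5% | 21% |

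If only half of the events were judged related, a true rate of 5% would give 1.5%. With all events recorded in both arms, equal 5% rates give p < 0.05 in 1.6% of trials. None of these rates comes from the protocol.

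**The case against.** Four points can be made on the other side.

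1. *SAEs are recorded in full.* Two sections say so plainly, and 8.3.6 describes the workflow. This stands. A reader might infer that every relative risk against U&CT is undefined, SAEs included. The documents do not support that: the forced zero reaches SAEs only through 8.3.4 item 1, and the defect there is a contradiction to be resolved.

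2. *No test is planned for non-serious AEs.* This also stands. A reader might infer from Step 3 that the trial is likely to declare a false safety difference. That would need 8.3.4 to override 8.3.5 and 8.3.6 and, in addition, a background SAE rate near 5% with the events called related. The protocol regards the risks as minimal (2.3.1) and its earlier studies report mainly minor skin irritation (2.2). At 1 to 2% the chance is negligible.

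3. *Other safety information lies outside the filter.* Section 8.2 also has therapist logs, weekly checks of the casted arm, and parent and child stress measures. This limits the damage. It does not repair the AE table, and the logs and cast checks have no U&CT counterpart.

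4. *The U&CT rule has a reason.* The study cannot investigate community therapy. That supports not attributing events to that therapy. It does not support barring events linked to study assessments, which the study itself carries out.

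The closer observation of I-ACQUIRE children over 20 sessions follows from the design and is not counted here as an error.

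**Conclusion.** The point holds for non-serious AEs and follows from the text alone, without any assumed rate: the U&CT count is 0/80 by rule, and the relative risks against U&CT planned in 8.2 and 9.4.5 cannot be interpreted. The U&CT rule also conflicts with the scope of causality assessment set in the same paragraph of 8.3.3.2.

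For SAEs the finding is narrower. Section 8.3.4 item 1 and the safety-report wording in 8.2 disagree with 8.3.5 and 8.3.6. Whether the Fisher test compares real rates depends on which section a site follows. The p-values and probabilities above are illustrations under that conditional reading and under assumed rates; they do not predict this trial.

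Severity: should fix. No efficacy conclusion and no binding stopping rule depends on this table, but as planned it would give the DSMB and the final report a control-arm figure that carries no information.

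**What to change.** 1. Amend 8.3.4 item 1 and the SAE wording in 8.2 to agree with 8.3.5 and 8.3.6, so that all SAEs are recorded in all arms regardless of relatedness. Without this edit the database rule would still contradict the comparison in item 2.
2. In 8.2 and 9.4.5, restrict relative risks and Fisher's tests against U&CT to events recorded regardless of relatedness: at minimum, all SAEs.
3. Report related non-serious AEs descriptively for the two I-ACQUIRE arms, with exact CIs and no relative risk against U&CT.
4. Narrow the 8.3.3.2 sentence to the U&CT therapy itself, so that an event linked to a study assessment or procedure can be judged related in any arm.

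The cost is wording in four sections (8.2, 8.3.3.2, 8.3.4, 9.4.5), with no new visits; sites already have to enter all SAEs under 8.3.5 and 8.3.6. The downside is that no relative risk against U&CT is reported for related non-serious AEs, but the current rules could not produce a usable one.
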